Trial Statisticians	[name]
	Lecturer in Biostatistics
	Biostatistics Research Group, Newcastle University
	[contact]
	[name] [name]
	Assistant Clinical Trials Statistician
	Biostatistics Research Group, Newcastle University
	[contact]
Sponsor	The Newcastle upon Tyne Hospitals NHS Foundation Trust
	Freeman Hospital
	[name]
	Newcastle upon Tyne
	[name]
	[contact]

Interventional I SarcoSIGHT	Non-CTIMP Protocol Template; version 1.0; dated 14 September	r 2015 IRAS 324220
Funder(s)	NIHR Efficacy and Mechanism Evaluation (EME) NIHR Evaluation, Trials and Studies Coordinating Centre University of Southampton [name]	
Collaborators/Co- Investigators	[name] Clinical Research Fellow The Newcastle upon Tyne Hospitals NHS Foundation Trust [contact]	
	[name] Head of the Academic Cardiovascular Unit South Tees NHS Foundation Trust [contact]	
	[name] Professor of Biostatistics Newcastle University [contact]	
	[name] Research Associate Newcastle Clinical Trials Unit [contact]	
	[name] Consultant Orthopaedic Surgeon Royal National Orthopaedic Hospital NHS Trust London [contact]	
	[name] Consultant Orthopaedic Surgeon Royal Orthopaedic Hospital NHS Foundation Trust Birmingham [contact]	
	[name] Consultant Plastic and Reconstructive Surgeon The Newcastle upon Tyne NHS Foundation Trust [contact]	

[name]
Professor of Precision and Molecular Pathology
Newcastle University
[contact]

[name] Academic Clinical Fellow in Orthopaedic Surgery Newcastle University [contact]

[name] Professor of Surgery University College Dublin [contact]

Committees

Chair of TSC [name] Consultant in Paediatric Surgery Birmingham Women's and Children's NHS Foundation Trust [contact]

Chair of DMC [name] Consultant Hepatobiliary Surgeon Liverpool University Hospitals NHS Foundation Trust [contact]

Chair of TMG [name] Trials Manager Newcastle Clinical Trials Unit [contact]

Trial Title	SarcoSIGHT: A Randomised-Control Trial of Fluorescence Guided			
	Sarcoma Surgery Versus the Standard of Care			
Acronym	SarcoSIGHT			
Summary of Trial Design	A prospective, 2-arm, open-label, U	IK multi-centre, randomised control		
	trial comparing fluorescence-guide	d surgery (FGS) with indocyanine		
	green (ICG) to standard care (no flu	orescence guidance) to determine		
	the effect on the unexpected positi	ve margin rate (UPM) in patients		
	with sarcoma.			
Summary of Participant	Patients of all ages with a histologic	cally confirmed diagnosis of		
Population	intermediate to high-grade bone or	soft tissue sarcoma suitable for		
	curative resection.			
Planned Sample Size	Total n=500 (FGS with ICG n=250, S	tandard Care n=250)		
Planned Number of	Up to 20			
Sites				
Intervention Duration	12–24-hour time period between t	ne administration of intravenous		
	(IV) ICG and the start of the resection.			
Follow Up Duration	Patients will be followed up for 12 months following the procedure,			
	with the option of an additional time point at 5 years if further funding			
	is secured.			
Planned Trial Period	58 months (7 months setup, 30 mo	nths of recruitment, 3 months		
	surgical delay, 12 months follow up	, 6 months final		
	report/dissemination)			
	Objectives Outcome Measures			
Primary	To determine whether FGS using	The UPM rate, defined as the		
	ICG reduces the UPM rate	percentage of patients with an		
	compared to the current standard	unexpected positive margin, will		
	of care (SoC).	be compared between the two		
	treatment arms.			
Secondary	Complications	Rates of intra- and postoperative		
	complications as recorded in the			
	clinical notes.			
	Length of index operation Difference in length of operation			
	in minutes.			

TRIAL SUMMARY

	Length of inpatient stay	Difference in length of inpatient stay in days.			
	Perceived impact of intervention in surgical decision making	The percentage of operations in which the surgeon stated FGS changed their planned resection.			
	Local recurrence (LR) rate	The difference in rate of local recurrence at 12 months.			
	Regional/distal recurrence rate	The difference in rate of regional/distal recurrence at 12 months.			
	Overall survival (OS) rate	The difference in rate of overall survival at 12 months.			
	Identify rates of adjuvant and neo-adjuvant therapies	Rates of adjuvant and neo- adjuvant therapies as per clinical notes.			
	Quality of life (QoL) measurements	The difference in scores on EQ- 5D-5L/EQ-5D-Y.			
	Recovery following resection	The difference in scores on the Toronto extremity salvage score (TESS)/ Paediatric Toronto extremity salvage score (pTESS)			
Exploratory Objectives	To determine the role of ICG in the pathological margin assessment of resected sarcoma specimens	Fluorescence microscopy to assess extracellular and cellular ICG spatial orientation in tumour tissue versus surrounding normal tissues			
	To develop artificial intelligence algorithms to improve the interpretation of fluorescence	Fluorescence mapping will be performed on all images taken during the trial and correlated with the pathological margin assessments			
Intervention	Standard care: the resection will b surgeon's standard procedure, wit will be based on the relevant pre-c	hout fluorescence guidance. This			
	FGS with ICG: Patients will be administered 1mg/kg of ICG intravenously (IV) 12-24 hours pre-operatively. Only the Stryker SPY-PHI near-infrared camera will be used for the intervention arm.				

Stryker will work with the SarcoSIGHT team to bring cameras to sites
that do not already have one available. If camera from a different
manufacturer is used this will be a protocol deviation and the
participant will need to be withdrawn from the trial. The Stryker SPY-
PHI camera will be used to image periodically throughout the
resection; any decision to make changes to the planned operative
procedure as a result of this will be at the discretion of the operating
surgeon.

Contents

RESEARCH REFERENCE NUMBERS
SIGNATURE PAGE
KEY TRIAL CONTACTS
TRIAL SUMMARY7
GLOSSARY OF ABBREVIATIONS

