3.2. Outcome Measures

3.2.1. Primary outcome measure

The primary outcome measure is the UPM rate. The margin status of each tumour will be taken from the pathology report for each patient enrolled in the trial. This will be recorded at six months postsurgery and will be classified according to the R classification system.⁶ Positive margins will be classified as the visualisation of tumour cells at the inked margin and will then be classified as acceptable or unexpected. The UPM rate for each arm will be defined by calculating the percentage of patients in that arm with a UPM on histopathological assessment of the resection specimen. If a negative margin is recorded, the size of the closest margin should be recorded in millimetres.

In this trial, the estimand aims to answer the research question: does fluorescence-guided surgery using indocyanine green (ICG) reduce the UPM compared to the standard of care (SoC)?

Estimand attribute	Description
Treatment	Fluorescence guided surgery (FGS) using indocyanine green (ICG) compared to standard of care (SoC) surgery
Population	Patients of all ages with a histologically confirmed diagnosis of intermediate to high grade bone or soft tissue sarcoma suitable for curative resection
Variable (outcome)	Unexpected positive margin (UPM)
Intercurrent events	There are no anticipated intercurrent events with respect to the observation of the primary outcome
Population-level summary measure	The difference in the UPM rates between the FGS group and SoC group

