7.8. Withdrawal Criteria

Participants have the right to withdraw from the trial at any time without giving a reason. Investigator sites should try to ascertain the reason for withdrawal and document this reason within the eCRF and participants' medical notes.

The Investigator may discontinue a participant from the trial at any time if the Investigator considers it necessary for any reason including:

- Symptomatic deterioration
- Participant withdrawal of consent
- Significant protocol deviation or non-compliance
- Investigator's discretion that it is in the best interest of the participant to withdraw
- An adverse event that requires discontinuation of the trial intervention or renders the participant unable to continue in the trial
- Termination of the clinical trial by the sponsor

Participants who withdraw from the trial prior to intervention will be replaced, whilst those withdrawing following the procedure will not.

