10. STATISTICAL CONSIDERATIONS

10.1. Analysis Population

Patients of all ages with a histologically confirmed diagnosis of intermediate- to high-grade bone or soft tissue sarcoma suitable for curative resection who meet the inclusion and exclusion criteria.

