10.2. Statistical Analyses

10.2.1. Analysis of the Primary Outcome Measure

Once margin data has been collected for 250 patients, an interim analysis will be conducted using a Barnard test to calculate a one-sided p-value, with non-binding stopping rules for both overwhelming efficacy and futility with regards to the primary outcome. The final analysis will then occur either after the interim analysis (if the trial stops) with all participants that have been recruited by the time the interim decision is made, or after the full target enrolment is reached (if the trial does not stop). All participants will be followed up for all outcomes, with final data cleaning and database lock occurring after that time. The primary analysis will be based on the Intention-to-treat (ITT) population with all participants included in the group they were randomised to. We do not anticipate a significant number of noncompliance and cross-over issues. If we encounter any protocol deviations or violations related to the treatment allocation, we will also define a perprotocol (PP) population for secondary analyses, in which participants for whom the allocated strategy was not followed will be excluded. All analyses will be described in a Statistical Analysis Plan (SAP) that will be finalised prior to trial statisticians receiving any unblinded data. For the analysis of the primary outcome, UPM rate, we will use a logistic regression that adjusts for key covariates including stratification factors used in the randomisation. A Wald test and a 95% confidence interval will be extracted from this model. A two-sided p-value will be found from the Wald test, although ICG will only be recommended as efficacious if the one-sided p-value for superiority of ICG is <0.0227.

Secondary analyses for the primary outcome will include the per-protocol population and a method that can account for the learning effect such as the hierarchical model approach proposed by Cook

et al ³⁶. Since the UPM rate is measured quickly after randomisation, we anticipate very low missing outcome data. Nevertheless, if this rate is higher than 5%, we will investigate applying a suitable missing at random (MAR) approach such as multiple imputation.

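### The instruction to withdraw FGS patients operated on with another camera conflicts with the intention-to-treat analysis and can lose primary outcomes in one arm only

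*Protocol*

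**What the plan says.** **Trial Summary, Intervention.** "Only the Stryker SPY-PHI near-infrared camera will be used for the intervention arm". Use of another manufacturer's camera is called a protocol deviation, and the "participant will need to be withdrawn from the trial".

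**Section 7.8.** The investigator may discontinue a participant for reasons that include "Significant protocol deviation or non-compliance". The section adds: "Participants who withdraw from the trial prior to intervention will be replaced, whilst those withdrawing following the procedure will not". It does not say whether margin status is still collected after withdrawal, or whether a replaced participant stays in the analysis.

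**Section 10.2.1.** "The primary analysis will be based on the Intention-to-treat (ITT) population with all participants included in the group they were randomised to". If there are deviations related to treatment allocation, a per-protocol set will be defined for secondary analyses, "in which participants for whom the allocated strategy was not followed will be excluded".

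**Section 3.2.1.** Margin status is taken from the pathology report and recorded at six months. The estimand table states: "There are no anticipated intercurrent events with respect to the observation of the primary outcome".

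**Section 8.1.3.** In both arms the specimen goes to histopathology as standard practice. The surgical team completes the trial pathology form after the MDT has discussed the report.

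**The concern.** The protocol handles one event in two ways. Under the Trial Summary, a patient imaged with another camera leaves the trial. Under Section 10.2.1, the same patient stays in the primary analysis in the FGS group and is left out only of the per-protocol set.

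A statistical analysis plan cannot fully repair this. It can define an ITT set, but it cannot restore outcomes that sites stopped recording. The camera is used during surgery, whereas margin status is entered later, so an instruction to withdraw takes effect before the primary outcome reaches the database. Because control surgery uses no fluorescence camera, any such loss falls in the FGS arm alone. If the patients lost differ in margin risk from those who remain, the comparison of UPM rates shifts for a reason unrelated to treatment.

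**Working it through.** **1. The passages side by side**

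| Question | Trial Summary / 7.8 | 10.2.1 |
|---|---|---|
| Is a patient imaged with another camera still in the trial? | No, withdrawn | Yes, analysed as randomised |
| Where is the deviation handled? | By leaving the trial | By exclusion from per-protocol only |
| Is margin status still collected? | Not stated | All participants to be followed for all outcomes |

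The first two rows conflict. The third shows how the conflict could cost data.

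**2. Inputs**

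- UPM 13.8% (standard care) and 5.1% (FGS), and 480 inflated to 500: Section 10.3.
- 250 per arm: Trial Summary.
- One-sided threshold 0.0227: Section 10.2.1.
- Number removed, k, and their UPM risk, m: not in the protocol; assumed here and varied.

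**3. The plan's own figure**

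The protocol gives no figure for camera deviations. Its sample size serves as a check on the inputs. With the pooled two-proportion formula, 90% power and one-sided 0.0227, the total is 484 for 13.8% against 5.1%, and 470 for 13.8% against 5%. These bracket 480. The dropout step is 480 / 0.96 = 500.

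**4. Effect of removing patients from one arm when there is no true effect**

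With 13.8% in both arms, 250 FGS patients carry 250 × 0.138 = 34.5 expected UPMs. After k are removed, the remaining FGS rate is

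r = (34.5 − k·m) / (250 − k).

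The false-positive rate is the exact binomial probability that a pooled z-test of 250 controls at 13.8% against 250 − k FGS patients at r passes one-sided 0.0227. With nobody removed it is 2.2%.

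| k | m | r | False-positive rate |
|---|---|---|---|
| 10 | 6.9% (half) | 33.81/240 = 14.1% | 1.8% |
| 10 | 13.8% (average) | 33.12/240 = 13.8% | 2.2% |
| 10 | 27.6% (double) | 31.74/240 = 13.2% | 3.5% |
| 10 | 40% | 30.5/240 = 12.7% | 5.0% |
| 25 | 6.9% | 32.775/225 = 14.6% | 1.3% |
| 25 | 27.6% | 27.6/225 = 12.3% | 6.6% |
| 25 | 40% | 24.5/225 = 10.9% | 14.9% |

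The rows with k = 25 (10% of the arm) are an extreme case. This is a single-stage, unadjusted calculation. The planned analysis is an adjusted logistic regression after an interim look, so the figures show sensitivity and are not a forecast.

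**5. Would the missing-data plan catch it?**

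Section 10.2.1 considers a missing-at-random method if more than 5% of outcomes are missing. Ten FGS removals are 10/250 = 4% of that arm but 10/500 = 2% of the trial. Read as an overall rate, the trigger would not be reached by these removals alone.

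**6. Power cost of keeping them**

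Assume k FGS patients stay in ITT and gain no benefit (13.8%). For k = 10 the FGS rate is (240 × 5.1% + 10 × 13.8%) / 250 = 5.45%. By the same exact method, power is 92.0% for k = 0, 89.1% for k = 10 and 83.6% for k = 25.

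**The case against.** The strongest reply is that withdrawal from the trial is not removal from the analysis. Section 10.2.1 sets the analysis rule, keeps everyone as randomised, expects few compliance problems and says all participants will be followed for all outcomes. On that reading the patient is in ITT, perhaps with a missing outcome. The event should also be rare, since the manufacturer is to bring cameras to sites without one, and camera availability may have nothing to do with margin risk. This stands as a limit on size. It does not settle the wording: a site told to withdraw a patient has no instruction to go on recording margin status.

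A reader might infer more than the documents support:

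- **That replacement breaches ITT.** The replacement rule in Section 7.8 applies to both arms and does not say that the original participant leaves the analysis. It is silent, not contradictory.
- **That Section 10.1 shrinks the analysis set.** It describes patients "suitable for curative resection who meet the inclusion and exclusion criteria". Section 7.3 allows randomisation only after eligibility is confirmed, so by design this is largely the randomised population.
- **That the estimand table is flatly contradicted.** Not anticipating an event is compatible with having a rule for it. The row sits awkwardly beside the camera rule, no more.
- **That the randomised comparison is destroyed.** At average risk there is no bias, and below-average risk makes the test conservative.

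**Conclusion.** The camera rule is wrong as written. It requires a post-randomisation withdrawal that only the FGS arm can experience, and it conflicts with the ITT and per-protocol rules in Section 10.2.1. Because neither the Trial Summary nor Section 7.8 separates stopping the intervention from stopping data collection, a primary outcome that routine pathology supplies may go unrecorded.

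The size cannot be fixed from the protocol. Ten removals move the false-positive rate to between 1.8% and 5.0% over the assumed risks, against 2.2% with none. Twenty-five, an extreme assumption, give 1.3% to 14.9%. The direction depends on whether the removed patients have lower or higher margin risk than the rest. Correction is still warranted, because an outcome not collected may be unrecoverable at analysis and the repair is cheap.

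**What to change.** 1. **Trial Summary, Intervention.** Replace the withdrawal instruction: use of another manufacturer's camera is a protocol deviation; margin status and all follow-up are still collected; the participant is analysed as randomised in ITT and excluded only from the per-protocol set.
2. **Section 7.8.** Separate stopping the trial intervention from withdrawing consent to data collection. State that replacements are added to the originally randomised participants in ITT and do not substitute for them.
3. **Section 3.2.1, estimand table.** As a consistency edit, name use of another camera as an intercurrent event under a treatment-policy strategy.

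None of this changes which camera the protocol requires or how patients are treated. The cost is protocol wording and slight dilution of the effect: power of about 89% instead of 92% if 10 of 250 FGS patients gain no benefit.

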16.4 Appendix 4. Calvien-Dindo Classification of Surgical Complications	

GLOSSARY OF ABBREVIATIONS

ABBREVIATION	DEFINITION
AE	Adverse Event
AR	Adverse Reaction
CI	Chief Investigator
CRF	Case Report Form
CRN	Clinical Research Network
DMC	Data Monitoring Committee
DPA	Data Protection Act
FGS	Fluorescence Guided Surgery
eCRF	Electronic Case Report Form
GCP	Good Clinical Practice
GDPR	General Data Protection Regulations
HRA	Health Research Authority
НТА	Human Tissue Authority
HTAct	Human Tissue Act
ICF	Informed Consent Form
ICG	Indocyanine Green
ID	Identification code
ISF	Investigator Site File
ISRCTN	International Standard Randomised Controlled Trials Number
ITT	Intention to Treat
IV	Intravenous
LR	Local Recurrence
MAR	Missing at Random

NCTU	Newcastle Clinical Trials Unit
NENC	North East and North Cumbria
NIHR	National Institute for Health and Care Research
NIHR CRN	National Institute for Health and Care Research Clinical Research Network Efficacy and Mechanism Evaluation
NIHR EME	National Institute for Health and Care Research Efficacy and Mechanism Evaluation
NHS	National Health Service
NUTH	The Newcastle upon Tyne Hospitals NHS Foundation Trust (Lead site)
OS	Overall Survival
PI	Principal Investigator
PIS	Participant Information Sheet
РР	per Protocol Population
pTESS	Paediatric Toronto Extremity Salvage Score
QC	Quality Control
QoL	Quality of Life
R&D	Research & Development
RACT	Risk Assessment Categorisation Tool
RCT	Randomised Control Trial
REC	Research Ethics Committee
RSE	Related Serious Event
SAE	Serious Adverse Event
SAP	Statistical Analysis Plan
SAR	Serious Adverse Reaction
SoC	Standard of Care
SOP	Standard Operating Procedure
SmPC	Summary of Product Characteristics

TESS	Toronto Extremity Salvage Score
TMF	Trial Master File
TMG	Trial Management Group
TSC	Trial Steering Committee
UPM	Unexpected Positive Margin
URSE	Unexpected Related Serious Event
USB	Universal Serial Bus (*N.B. apparatus for transferring data, usually referred to as a 'USB stick')
USM	Urgent Safety Measure

1. BACKGROUND

Sarcomas are rare malignant tumours accounting for 1% of all cancers with around 5300 patients diagnosed annually in the UK.¹ Sarcomas affect a wide age range of the population with the highest incidence of some sub-types in children and the overall prevalence affecting a younger age group than other cancers. The median age of patients at diagnosis is 56 years, which is lower than most other cancer types.² Sarcomas are heterogenous with at least 70 different sub-types arising from soft tissues and bone, most commonly occurring in the extremities.³ Survival is poor, with a five year survival rate of approximately 65%, reducing to 50% in higher grade sarcomas, with little improvement in survival outcomes over the last 30 years.⁴ Surgery is the mainstay of treatment, with the goal being complete resection of the tumour whilst leaving as much normal tissue as possible to maximise functional outcomes. Many of these operations are complex, often requiring input from surgeons from more than one specialty and resulting in major functional compromise to the patient due to the volumes of tissue that need to be resected. Currently, surgeons use pre-operative imaging to plan the resection of the tumour and operate by eye and palpation but have no other intra-operative options to guide the surgery. This often leads to uncertainty during the operation, particularly in difficult anatomical locations, as to where the tumour ends and normal tissue begins.⁵

1.1. MARGINS

The most important prognostic factor surgically is the resection margin. Margins are assessed postoperatively by a pathologist. A clear margin, known as a negative margin, means that the resected tumour is surrounded by normal tissue, which implies there is no disease left in the patient. By contrast, a positive margin means that sarcoma cells are visible at the edge of the tumour. Positive margins can be either macroscopic or microscopic; macroscopic mean that tumour can be seen at the edge of the specimen with the naked eye, whereas microscopic means a microscope is required to visualise tumour cells at the margin. Sarcoma margins are most commonly defined by the R classification system,⁶ with both positive macroscopic and microscopic margins associated with increased local recurrence (LR) and decreased overall survival (OS).⁷⁻⁹ Positive margins may be classified as either planned when they are expected pre-operatively due to the preservation of a critical structure as seen on images or unexpected, when the pathologist reports the presence of tumour at the margin despite the surgeon having intended to remove it in its entirety. The latter classification, known as an unexpected positive margin (UPM) is associated with worse oncological outcomes.^{8,9} The histological grade assigned to the tumour is also important, with high grade tumours not only carrying a worse prognosis, but also being associated with higher rates of positive margins.¹⁰

The reported positive margin rate varies widely in the literature, with quoted values between 8% and 29.9%.^{7,8,10-14} The largest of these studies reported the percentage of patients who have a UPM on histopathological assessment of the resection specimen (known as UPM rate) as 9% (n=2217).⁸ Analysis of 224 patients with intermediate to high grade bone and soft tissue sarcomas at the North of England Bone and Soft Tissue Tumour Service in a five-year period between 2010 and 2015 found a UPM rate of 13.8% (n=224). Figure 1 includes data from this cohort and demonstrates that positive margins significantly correlate with a higher rate of local recurrence, reduced time to local recurrence and poorer overall survival.

Given that the positive margin rate remains considerable and has such clear associations with poor oncological outcomes, there is a requirement for technologies that will assist sarcoma surgeons to achieve lower positive margins rates, thereby improving both short- and long-term outcomes for patients.

Figure 1. a) Kaplan Meier plot of cumulative risk of local recurrence according to margin status. b) Kaplan Meier plot of overall survival

For the purposes of this trial, we will be renaming one of the margin statuses from that usually described in the literature. Whilst the terms 'negative' and 'unexpected positive' margins will be kept unchanged, 'planned positive' margins in the context of preserving a critical structure will instead be changed to 'acceptable close' or 'acceptable positive' margins, depending on the final histology. We felt the term 'planned positive' could be misleading to trial participants and stakeholders and could erroneously imply that patients were being included in the trial unnecessarily. See Section 2 for a complete outline of the margin terminology that will be used in this trial.

